Therefore, in order to avoid issues caused by inaccurate floating point representation of numeric values, temporary variables are created (ie, for absolute values, change and percentage change from Baseline) during programming which are rounded to 12 decimal places prior to comparison to a specific threshold in the derivation of a response parameter. This does not imply inherent rounding on the analysis variables for absolute value, change or percentage of change which are retained unrounded in the final analysis dataset. Thus, rounding is applied exclusively during the derivation of new response parameters or critical value variables, and the rounded values are created on a temporary basis only.

The SAS® outputs supportive of any inferential statistics that are part of the hierarchical testing procedure (ie, all inferential statistics associated with the endpoints in [Table 7–4](#) will be provided as a separate PDF document in addition to TFLs. These outputs will be included in the ‘Documentation of Statistical Methods’ section of the clinical study report.

The order of treatment groups to be presented in tables from left to right will be:

- Placebo
- Bimekizumab 160mg Q4W

Selected tables may also include columns for all subjects (regardless of study treatment).

The abbreviation for bimekizumab is BKZ and will be used in tables and listings headers. In the TLFs subjects randomized to bimekizumab 160mg will be labeled as “BKZ 160mg Q4W”.

Per protocol, visit windows of ± 3 days from the first dose at all visits through Week 16 are permissible. For the SFU Visit, the visit should occur no more than 3 days prior to the scheduled visit date and within 7 days after the scheduled visit date. Only data collected at the scheduled visit will be included in the analysis. The only deviation may concern unscheduled vendor data as explained in [Section 10.5](#).

All by-visit summaries will contain nominal (ie, scheduled) visits only. Unscheduled visits will not be mapped to scheduled visits except for some assessments that may occur within 3-day time window of a scheduled visit. In that case, the assessment will be mapped to the corresponding scheduled visit and will be used for the analysis unless the data are present for that scheduled visit.

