8.1.1.1 Derivation of tender joint count (TJC) and swollen joint count (SJC)

Tender and swollen joints are assessed based on the 68 and 66 joints for tenderness and swelling, respectively. The 68/66 joints that are assessed are:

- Upper body (6) - bilateral temporomandibular, sternoclavicular, and acromioclavicular joints.
- Upper extremity (34) - bilateral shoulders, elbows, wrists (includes radiocarpal, carpal and carpometacarpal bones considered as a single unit), metacarpophalangeal (I, II, III, IV, and V), thumb interphalangeals, proximal interphalangeal (II, III, IV, and V), and distal interphalangeals (II, III, IV, and V).
- Lower extremity (28) - bilateral hips, knees, ankles, tarsi (includes subtalar, transverse tarsal, and tarsometatarsal considered as a single unit), metatarsophalangeals (I, II, III, IV, and V), great toe interphalangeals, and proximal interphalangeals (II, III, IV, and V).

The assessment on swelling exclude the hips.

Each of the joints can be graded as follows by the assessor:

- Permanently not assessable
- Temporarily not assessable
- Asymptomatic
- Tender only
- Swollen only
- Tender and swollen

Permanently non-evaluable joints will be considered missing for both tender and swollen joint counts at the visit at which the grading was recorded and all subsequent visits. The asymptomatic joints will be included in the joint count analysis with scores of 0.

For the statistical analysis, swelling and tenderness will be each graded on a 2-point scale as described below in [Table 8–1](#).

Table 8–1: Swelling and Tenderness grading

Present	Tenderness response (68)	Swelling response (66)
No (0)	Not tender	None
Yes (1)	Positive response to questioning (tender), spontaneous response elicited (tender and winced) or withdrawal by subject on examination (tender, winced, and withdrew)	Detectable synovial thickening with or without loss of bony contours, or bulging synovial proliferation with or without cystic characteristics

The joint graded by the assessor will then have its grade mapped as follows:

- The “Tender only” joints will correspond to a tenderness response of 1, and a swelling response of 0.
- The “Swollen only” joints will correspond to a swelling response of 1, and a tenderness response of 0.
- The “Tender and swollen” joints will correspond to a swelling and tenderness response of 1.

Dactylitic digits will be identified as follows and the joints will be counted as follows:

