- Fingers 2-5: Swelling Distal Interphalangeal Joint x (side), Swelling Proximal Interphalangeal Joint x (side), Swelling Metacarpophalangeal Joint x (side) – if they are in any of the gradings ‘swollen-only’ or ‘tender and swelling’ or ‘injected’ then only 1 finger will be added to the swollen joint count
- Toes 1-5: Swelling Interphalangeal Joint x (side), Swelling Metatarsophalangeal Joint x (side) – if they were in any of gradings ‘swollen’ or ‘tender and swollen’ or ‘injected’ then only 1 toe will be added to the swollen joint count

The tender joint count (TJC) and swollen joint count (SJC) are weighted joint counts. If there are missing observations in the tender or swollen joint assessments (TJ and SJ, respectively), then the remaining observations will be assessed and weighted by the number of the assessed joints (AJ) as shown below:

$$TJC = n \times \frac{\sum_{i=1}^n TJ}{\sum_{i=1}^n AJ}$$

$$SJC = n \times \frac{\sum_{i=1}^n SJ}{\sum_{i=1}^n AJ}$$

Where n represents the number of total joints.

However, if a joint is missing at Baseline, then that joint will be set to missing throughout the study. If more than 50% of the planned tender joint assessments (ie, more than 34) or 50% of the

planned swollen joint assessments (ie, more than 33) are missing at any post-Baseline visit, then no imputation will be done and the total TJC or SJC will be set to missing for that visit.

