The norm-based T-scores for the 2 SF-36 component summary (PCS and MCS) and the 8 domains are standardized with a mean of 50 and a standard deviation (SD) of 10 in the general US population (Maruish, 2011). An individual respondent's score that falls outside the T-score range of 45 to 55 should be considered outside the average range for the US general population. When considering group-level data, a score below 47 should be considered indicative of impaired functioning within that health domain or dimension. Similar to individual respondent data, group mean scores of 47 or greater should be considered average or above average as compared to the general US population. Higher scores indicate a better health status.

For the calculation of the SF-36 norm-based T-scores for the 8 domains and the PCS and MCS, the scoring software Optum's PRO CoRE (version 1.4) will be used. The software uses updated 2009 U.S. population norms and applies a Full Missing Score Estimation method as follows:

- A health domain score (except the Physical Functioning domain) will be estimated provided that at least one non-missing response is available within that domain.
- For the Physical Functioning domain, item response theory will be used to develop a model for estimates of the missing score.
- Regression methods will then be applied to estimate the PCS and MCS on the basis of the available domains.

Change from Baseline at Week 16 in SF-36 PCS score is the 4th endpoint in the sequential testing hierarchy (Table 7-4).

8.2.1.4 MDA at Week 16

MDA is a state of disease activity deemed a useful target of treatment by both the subject and physician, given current treatment possibilities and limitations. The criteria that need to be met are based on key outcome measures in PsA and are shown below:

- Tender Joint Count ≤ 1
- Swollen Joint Count ≤ 1
- PASI ≤ 1 (for subjects with PSO involving at least 3% of BSA at Baseline) or BSA $\leq 3\%$
- PtAAP (VAS) ≤ 15 mm
- PGA-PsA (VAS) ≤ 20 mm
- HAQ-DI ≤ 0.5
- Tender enthesial points ≤ 1 (LEI ≤ 1)

A subject has achieved MDA if 5 or more of the 7 above criteria are fulfilled.

The enthesitis instrument of the study (ie., LEI) will be used to determine whether a subject has ≤ 1 tender enthesial point.

The following rule will be applied for subjects with BSA < 3 at Baseline: Subjects with BSA < 3 at Baseline will always meet the criteria PASI ≤ 1 or BSA ≤ 3 except in the cases where a post-Baseline BSA score > 3 is observed.

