8.3.1.12 Change from Baseline in all individual ACR core components

Individual ACR components (as listed in [Section 8.1.1](#)) are:

- SJC,
- TJC,
- HAQ-DI,
- PtAAP,
- PhGA-PsA,
- PGA-PsA,
- hs-CRP.

The change from Baseline (ratio from Baseline for hs-CRP) for each of the ACR components will be summarized at Week 4, 8, 12, and 16.

8.3.1.13 Enthesitis-free state based on the LEI and change in LEI from Baseline in the subgroup of subjects with enthesitis at Baseline

The Leeds Enthesitis Index (LEI) is an index composed of 6 items, 3 for the right part and 3 for the left part of the body that measures the severity of enthesitis. The body parts are lateral epicondyles of the humerus, medial femoral condyle, and Achilles tendons. Each item is scored for pain with either 1 (painful) or 0 (no pain). The total score ranges from 0 (no enthesitis) to 6 (severe enthesitis).

Note that LEI is collected for all subjects regardless of their Baseline score.

In case 4 items are missing, the LEI will be set to missing. If at least 3 items are available, the available items will be assessed and scored and then weighted by the number of the assessed items (AI) as shown in the formula below:

$$LEI = n \times \frac{\sum_{i=1}^n score}{\sum_{i=1}^n AI}$$

Note that n refers to the number of total items.

Enthesitis-free state is based on LEI of 0, for subjects with enthesitis at Baseline (LEI>0). Analyses on LEI will be restricted to the subset of subjects with enthesitis at Baseline (defined as LEI score>0).

The percentage of subjects with enthesitis free-state and the change from Baseline in LEI, in the subgroup of subjects with enthesitis at Baseline, will be analyzed at Week 4, 8, 12, and 16.

While not a secondary endpoint, to support the pooled endpoint in PA0010, enthesitis free-state at Week 16 will be analyzed using the same analysis method as the primary analysis.

8.3.1.14 Enthesitis-free state based on the SPARCC index and change in SPARCC index from Baseline in the subgroup of subjects with enthesitis at Baseline

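### MDA and VLDA compare prorated joint and entheseal counts with a cut-off of 1, so one active site plus one unassessed site fails the criterion; MDA status then changes only for subjects at the 5-of-7 margin

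*SAP*

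**What the plan says.** - **Joint counts.** Section 8.1.1.1: "The tender joint count (TJC) and swollen joint count (SJC) are weighted joint counts". Each is the number of joints (68 or 66) times active joints divided by assessed joints. It is set to missing only if more than 34 tender or 33 swollen assessments are missing.
- **Missing joints persist.** "Permanently non-evaluable joints will be considered missing for both tender and swollen joint counts" at that visit and all later ones. "However, if a joint is missing at Baseline, then that joint will be set to missing throughout the study".
- **LEI.** Section 8.3.1.13: "If at least 3 items are available, the available items will be assessed and scored and then weighted by the number of the assessed items", with 6 items in total.
- **MDA.** Section 8.2.1.4 lists "Tender Joint Count ≤ 1", the same limit for swollen joints, and at most one tender entheseal point, glossed in brackets as the LEI score. "A subject has achieved MDA if 5 or more of the 7 above criteria are fulfilled". VLDA (Section 8.3.1.8) needs all 7.
- **Rounding.** Section 3.1 creates temporary variables "which are rounded to 12 decimal places prior to comparison to a specific threshold in the derivation of a response parameter". The range table in Section 4.2.1 does not mark TJC, SJC or LEI as integer-valued.
- **Role.** MDA at Week 16 is H5, the last test in the fixed sequence (Section 4.5).

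**The concern.** Proration suits percent-change endpoints such as ACR, where the same scaling largely cancels between visits. It does not suit a cut-off at one site. Once any site is missing, a single active site gives a value just above 1, and nothing in the SAP brings it back to 1. A joint missing at Baseline stays missing, so such a subject can meet the joint criterion at Week 16 only with no active joint at all.

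The result is also inconsistent. A subject with 34 unassessed and no tender joints scores 0 and passes, while a subject with 1 unassessed and 1 tender joint fails. At stake are the responder status of some subjects on a confirmatory endpoint and, more directly, VLDA.

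**Working it through.** **1. The plan's own figure.** Section 2.4.2 gives 92% power for MDA, 17% vs 5%, with 260 vs 130 subjects, two-sided 0.05 and a continuity-corrected chi-square test.
- Odds ratio: (0.17/0.83)/(0.05/0.95) = 3.892, as stated.
- Correction term: c = (k+1)/(k·d) = 3/(2 × 0.12) = 12.5. The corrected placebo size of 130 corresponds to an uncorrected 130 − 12.5 + 12.5²/(4 × 130) = 117.8.
- Pooled rate: (0.05 + 2 × 0.17)/3 = 0.13.
- z = [0.12 × √117.8 − 1.96 × √(0.13 × 0.87 × 1.5)] / √(0.05 × 0.95 + 0.17 × 0.83/2) = (1.302 − 0.807)/0.344 = 1.44, so power is 92.5%. The stated 92% reproduces and is not in dispute.

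**2. The prorated value with exactly one active site** (total sites × 1 / assessed sites):

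| Sites missing | TJC | SJC | LEI |
|---|---|---|---|
| 0 | 1 (pass) | 1 (pass) | 1 (pass) |
| 1 | 68/67 = 1.0149 (fail) | 66/65 = 1.0154 (fail) | 6/5 = 1.2 (fail) |
| 2 | 68/66 = 1.0303 (fail) | 66/64 = 1.0313 (fail) | 6/4 = 1.5 (fail) |
| Most allowed | 68/34 = 2 (fail) | 66/33 = 2 (fail) | 6/3 = 2 (fail) |

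Rounding to 12 decimals changes none of these results. With no active site the value is 0 and passes whatever is missing. The LEI column assumes that the criterion uses the prorated score.

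**3. From criterion to endpoint.**
- *One criterion lost.* With 5 or 6 of the other 6 met, the subject is still an MDA responder. With exactly 4 met, MDA changes from 4 + 1 = 5 (response) to 4 (non-response). With 3 or fewer, the subject is a non-responder either way.
- *Two criteria lost* (one joint both tender and swollen, and another joint unassessed for both). With 3 or 4 of the other 5 met, MDA changes from 5 or 6 to 3 or 4. With all 5 met, the subject is still a responder.
- *VLDA.* Lost whenever all the other criteria are met.

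**4. Size.** The SAP gives neither the share of subjects with a missing joint nor the share at the 5-of-7 margin. As an assumption only, let the same fraction of MDA responders be lost in each arm:

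| Assumed loss | BKZ vs placebo rate | H5 power |
|---|---|---|
| 0% | 17.00% vs 5.00% | 92.5% |
| 1% | 16.83% vs 4.95% | 92.2% |
| 2% | 16.66% vs 4.90% | 91.8% |
| 5% | 16.15% vs 4.75% | 90.7% |
| 10% | 15.30% vs 4.50% | 88.5% |

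A 5% loss is 260 × 0.17 × 0.05 = 2.2 responders on BKZ and 130 × 0.05 × 0.05 = 0.3 on placebo.

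**The case against.** The best defence is that the unassessed site might itself be active. The true count is then 1 or 2, and failing the criterion is in keeping with an SAP that sends undecidable MDA cases to non-response (Section 8.2.2). The rule is the same in both arms and cannot favour BKZ under the null hypothesis. MDA also needs only 5 of 7 criteria, H5 has no test after it, and VLDA is outside the hierarchy.

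Most of this stands and limits the point. It does not make the rule sound. The SAP's own estimate for such a subject is 1.015 joints, whose nearest whole count is 1, and a deliberately conservative rule would not pass a subject with 34 unassessed joints.

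Two further objections also stand in part:
- **LEI.** Section 8.2.1.4 speaks of tender points, which reads as a count, and then of the LEI score, which is prorated. The two differ exactly when an item is missing, so this is an ambiguity and not a certain failure.
- **Imputed values.** A reader might infer that imputed counts between 1 and 1.5 also fail. Sections 4.2.2.2.1 and 4.2.2.2.2 do apply a rounding step after imputation. They define it as rounding to an integer only for endpoints marked integer, so for these three counts it is undefined. The multiple-imputation analysis of MDA is supportive only.

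**Conclusion.** The defect is certain at the level of the joint criteria: with any joint unassessed, the effective cut-off for TJC or SJC is 0 and not 1. A reader might infer that every such subject fails MDA and that H5 is misclassified as a whole. The SAP does not support that, because MDA changes only at the 5-of-7 margin set out above, and because the true count of a subject with an unassessed site is unknown.

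The number of subjects affected cannot be derived from the SAP and is probably small. On the assumed losses of 0% to 10% of MDA responders per arm, H5 power moves from 92.5% to 88.5%. The direction is against response in both arms, so the concern is some loss of sensitivity and an arbitrary responder rule, with no false-positive risk. VLDA is affected more directly, since a single lost criterion is decisive.

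**What to change.** In Sections 8.2.1.4 and 8.3.1.8, state that the prorated TJC and SJC, whether observed or imputed, are rounded to the nearest integer (halves up) before comparison with the cut-off of 1, and that the same applies to LEI. This also settles the LEI wording and the undefined rounding of imputed values for these criteria.

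One active site then passes with up to 22 missing tender joints (68/46 = 1.48), 21 missing swollen joints (66/45 = 1.47) or 1 missing LEI item (6/5 = 1.2). It still fails with 23 (68/45 = 1.51), 22 (66/44 = 1.5) or 2 (6/4 = 1.5).

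Do not switch to unweighted counts: these would treat up to 34 unassessed joints as inactive. Keep the unrounded prorated counts for ACR and the other change endpoints.

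The cost is a sentence in each of the two sections and one line of derivation code, to be settled before treatment codes are released for the Week 16 analysis. The downside is that a few subjects whose unassessed site was in fact active would be counted as meeting the criterion.

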8.1.1.2 Patient and physician reported clinical outcomes on psoriatic arthritis

The physician's global assessment of psoriatic arthritis (PhGA-PsA), the patient's global assessment of psoriatic arthritis (PGA-PsA) and the patient's assessment of arthritis pain (PtAAP) are clinical outcomes based on visual analog scales (VAS) ranged from 0 to 100 (in mm).

- PhGA-PsA: The investigator will assess the overall status of the subject with respect to their PsA signs and symptoms using a numerical rating scale where 0 is "very good, asymptomatic and no limitation of normal activities" and 100 is "very poor, very severe symptoms which are intolerable and inability to carry out all normal activities". This assessment will be based through the following question "Considering all the ways the disease affects your patient, mark a vertical line on the scale for how well his or her condition is today."
- PGA-PsA: Subjects will assess the impact of PsA in answering the following question "Considering all the ways your psoriatic arthritis affects you, please mark a vertical line on the scale below to show how well you are doing today." The subject should be asked to consider all aspects of their disease (including joint and skin components) in their response to this question. Subjects will score PGA-PsA in using a VAS where 0 is "very good, no symptoms" and 100 is "very poor, severe symptoms."
- PtAAP: Subjects will assess their arthritis pain through the PtAAP using a VAS where 0 is "no pain" and 100 is "most severe pain."

8.1.1.3 Derivation of the health assessment questionnaire disability index score (HAQ-DI)

The HAQ-DI contains 20 items that measure the degree of difficulty experienced in the following 8 categories of the daily living activities: dressing and grooming (2 items), arising (2 items), eating (3 items), walking (2 items), hygiene (3 items), reach (2 items), grip (3 items), and common daily activities (3 items).

For each question/item, subjects should indicate the level of difficulty (from 0 to 3) in the past week as follows:

- 0: 'without any difficulty'
- 1: 'with some difficulty'
- 2: 'with much difficulty'
- 3: 'unable to do'

Each category is given a score by taking the maximum value for each question.

For each question related to a specific daily living activity, subjects can specify whether an aid or devices is usually used.

If a category score equals 0 or 1, but a device related to that category is used, or help from another person is provided for that category, then the category score is increased to 2.

If a category score already equals 2, and a device related to that category is used, or help from another person is provided for that category, the score for that category remains 2.

Table 8–2 details how each aid and device is associated with the category scores. Aid or device considered as ‘other’ than the ones listed will not be considered in the analysis.

Table 8–2: Aid and device associated with HAQ-DI category

Aid or device	Will be associated with category score
[REDACTED]	Walking
	Dressing and grooming
	Eating
	Arising
	Hygiene
	Hygiene
	Grip
	Hygiene
	Reach
	Hygiene

If all questions within a given category are unanswered, no score will be provided for that category (this rule applies even if aids and devices are non-missing).

The HAQ-DI score will be calculated by dividing the sum of the highest category scores (0 to 24) by the number of categories with at least 1 question answered. If fewer than 6 categories have responses, no HAQ-DI score will be calculated (ie, HAQ-DI score will be considered missing).

The HAQ-DI score ranges from 0 to 3. A lower HAQ-DI score indicates an improvement in function.

8.1.1.4 High-sensitivity C-Reactive Protein (hs-CRP)

In the summary tables presenting hs-CRP values, the observed values and ratio to Baseline values will be displayed.

hs-CRP values which are below the lower limit of quantification (LLOQ) should be set to the midpoint between 0 and the LLOQ prior to the analysis. Listing will show values below the LLOQ. The LLOQ for hs-CRP is 0.10mg/L.

8.1.2 Primary analysis of the primary efficacy variable

The primary efficacy variable will be analyzed for all subjects in the RS.

The primary endpoint is the ACR50 response at Week 16. The primary efficacy analysis will evaluate the composite estimand in the RS. The composite estimand combines the clinically meaningful improvement from Baseline in ACR components as assessed using the ACR50 response at Week 16 and not discontinuing study treatment prior to Week 16.

The following 4 attributes describe the estimand that will be used to define the treatment effect of interest for the primary efficacy analysis:

- Population = Subjects enrolled according to the protocol-specified inclusion/exclusion criteria and randomized to IMP
- Subject-level outcome = ACR50 at Week 16
- Intercurrent event handling = An intercurrent event is defined as discontinuation of study treatment prior to Week 16. A composite strategy will be implemented in which a positive clinical outcome is defined as achieving ACR50 at Week 16 and not discontinuing study treatment through Week 16.
- Population-level summary measure = Conditional odds ratio comparing BKZ to placebo and difference of response rate between BKZ and placebo.

Missing data at Week 16 that are not preceded by an IE and any data after an IE will be imputed as non-responders. This results in a more traditional NRI approach and will be labeled as such throughout the SAP.

The statistical hypothesis for the ACR50 response at Week 16 is that the conditional OR for ACR50 response in the BKZ treatment compared to placebo treatment is equal to 1.

A logistic regression model will be used to assess the treatment effect on ACR50 response at Week 16. The model will include fixed effects for treatment, and prior TNF α inhibitor exposure and region as stratification factors. The suitability of including these variables in the model will be assessed using Pearson and Deviance and the Hosmer-Lemeshow Goodness-of-Fit Tests (Hosmer and Lemeshow, 2000).

P-values below 0.05 would lead to a reconsideration of the model to be used and if the logistic regression model is unable to converge the stratification variables will be dropped ([Section 4.1](#)). In that case, all supportive analyses as well as imputation models conducted for the primary endpoint will disregard these exploratory factors from their models.

The country-specific analyses performed on subjects randomized in Japan will not consider the region factor as a covariate for the modelling. Considering that the number of subjects randomized in Japan is low (less of 10% of the RS), statistical models might not converge. If a model (logistic Model or mixed model) is not converging, all related adjusted statistics and p-value will not be presented; “NE” for “Not Evaluable” will be displayed instead.

The SAS® PROC LOGISTIC will be used to run the logistic regression.

The summary table results will present the adjusted responder rates and the associated 95% CI for BKZ and placebo, the adjusted odds ratio and 95% CI for the comparison of BKZ versus placebo, and the p-value that the OR=1 and the difference of response rate between BKZ and placebo and associated 95% CI. The treatment comparison will be made using the 2-sided Wald test at a significance level of $\alpha=0.05$ (ie, H_1 in [Table 7-4](#)).

